10.7 Appendix 7: Pharmacogenomic Analysis with Banked Sample

INTRODUCTION

PGx research aims to provide information regarding how naturally occurring differences in a participant's gene and/or expression of genes based on genetic variation may impact what treatment options are best suited for the participant. Through investigation of PGx by technologies such as genotyping, gene sequencing, statistical genetics and Genome-Wide Association studies, the relationship between gene profiles and a drug's kinetics, efficacy, toxicity or disease may be better understood. As many diseases may be influenced by one or more genetic variations, PGx research may identify which genes are involved in determining the way a participant may or may not respond to a drug.

OBJECTIVES

The PGx research that may be conducted in the future with acquired blood samples is exploratory. The objective of this research will be to analyze or determine genes of relevance to clinical response, pharmacokinetics and/or toxicity/safety and/or disease.

By analyzing genetic variations, it may be possible to predict an individual participant's response to treatment in terms of efficacy and/or toxicity and/or disease.

PARTICIPANT PARTICIPATION

Participants who have consented to participate in this study will participate in the PGx substudy. Participants must provide written consent prior to providing any blood samples that may be used at a later time for PGx analysis.

SAMPLE COLLECTION AND STORAGE

Participants who consent to participate in this substudy will provide approximately 4 mL sample of whole blood per Astellas' instructions. Each sample will be identified by the unique participant number. Samples will be shipped to a designated banking CRO as directed by Astellas.

PGx ANALYSIS

Details on the potential PGx analysis cannot be established yet. Astellas may initiate the PGx analysis if evidence suggests that genetic variants may be influencing the drug's pharmacokinetics, efficacy and/or safety and/or disease.

DISPOSAL OF PGx SAMPLES/DATA

All PGx samples collected will be stored for a period of up to 15 years following study database lock. If there is no requirement for analysis, the whole blood sample will be destroyed after the planned storage period. The participant has the right to withdraw consent at any time. When a participant's withdraw notification is received, the PGx sample will be destroyed. The results of any PGx analysis conducted on a sample prior to its withdrawal will be retained at Astellas indefinitely unless otherwise specified by local regulation.

INFORMATION DISCLOSURE TO THE PARTICIPANTS

Exploratory PGx analysis may be conducted following the conclusion of the study, if applicable. The results of the PGx analysis will not be provided to any investigators or participants, nor can the results be requested at a later date. Any information that is obtained from the PGx analysis will be the property of Astellas.

10.8 Appendix 8: Infusion Reaction Dose Modification and Treatment (Guidelines for ASP0739 and Pembrolizumab)

Table 14 Infusion Reaction Dose Modification and Treatment (Guidelines for ASP0739 and Pembrolizumab)

NCI-CTCAE Grade	Treatment	Premedication at Subsequent Dosing
Grade 1 Mild reaction; infusion interruption not indicated; intervention not indicated	
Increase monitoring of vital signs as medically indicated until the participant is deemed medically stable in the opinion of the investigator.	None
Grade 2 Requires therapy or infusion interruption but responds promptly to symptomatic treatment (e.g., antihistamines, NSAIDs, narcotics, intravenous fluids); prophylactic medications indicated for \leq 24 hours.	
Stop Infusion.Additional appropriate medical therapy may include but is not limited to:
Intravenous fluidsAntihistaminesNSAIDsAcetaminophenNarcoticsIncrease monitoring of vital signs as medically indicated until the participant is deemed medically stable in the opinion of the investigator.If symptoms resolve within 1 hr of stopping drug infusion, the infusion may be restarted at 50% of the original infusion rate (e.g., from 100 mL/hr. to 50 mL/hr.). Otherwise, dosing will be held until symptoms resolve and the participant should be premedicated for the next scheduled dose. 
Participants who develop grade 2 toxicity despite adequate premedication should be permanently discontinued from further treatment (pembrolizumab only)
	
Pembrolizumab only: Participant may be premedicated 1.5 hours (\pm 30 min) prior to infusion of pembrolizumab with: Diphenhydramine 50 mg po (or equivalent dose of antihistamine). Acetaminophen 500 to 1000 mg po (or equivalent dose of analgesic).
 
Contact the study medical monitor regarding ASP0739 dose management

Table continued on next page

NCI-CTCAE Grade	Treatment	Premedication at Subsequent Dosing
Grades 3 or 4 Grade 3: Prolonged (i.e., not rapidly responsive to symptomatic medication and/or brief interruption of infusion); recurrence of symptoms following initial improvement; hospitalization indicated for other clinical sequelae (e.g., renal impairment, pulmonary infiltrates) Grade 4: Life-threatening; pressor or ventilator support indicated	
 Stop Infusion. Additional appropriate medical therapy may include, but is not limited to: 
 Epinephrine* Intravenous fluids Antihistamines NSAIDs Acetaminophen Narcotics Oxygen Pressors Corticosteroids Increase monitoring of vital signs as medically indicated until the participant is deemed medically stable in the opinion of the investigator. Once the participant has been stabilized, collect blood for cytokine/chemokine panel (ad hoc collection for shipment to central lab). If the reaction is suggestive of anaphylaxis, collect blood (standard red top tube) for serum total tryptase level (levels typically peak within 3 hours after the onset of symptoms). Serum should be frozen if the assay cannot be performed promptly at the local laboratory. Hospitalization may be indicated. 
* In cases of anaphylaxis, epinephrine should be used immediately. Participant is permanently discontinued from further study drug treatment.
	Any grade 4 hypersensitivity reaction/anaphylaxis, study treatment should be discontinued

Appropriate resuscitation equipment should be available at the bedside and a physician readily available during the period of drug administration. For further information, please refer to the Common Terminology Criteria for Adverse Events v5.0 (CTCAE) at <http://ctep.cancer.gov>.

hr: hour; NCI: National Cancer Institute; NSAID: non-steroidal anti-inflammatory drug; po: by mouth

10.9 Appendix 9: Monitoring of Pembrolizumab Potential Immune-related Adverse Events

Table 15 Monitoring of Pembrolizumab Potential Immune-related Adverse Events

Potential irAE	Closely monitor participants' symptoms for prompt diagnosis and management.
Pneumonitis	New cough, worsening cough, shortness of breath, or chest pain
Colitis	Changes in bowel habits; abdominal pain; blood or mucus in stool; nausea
Hepatitis	Yellowing of skin or whites of eyes; pain on right side of abdomen; dark urine (color of tea); nausea or vomiting; bleeding or bruising more easily than usual; loss of appetite; drowsiness
Endocrinopathies	Persistent or unusual headaches, changes in vision, rapid heartbeat, increased sweating, feeling very tired or weak, achy muscles, change in weight (gain or loss), feeling lightheaded or feeling faint, feeling more hungry or thirsty than usual, loss of hair, mood changes such as reduced sex drive or increased irritability, forgetfulness, feeling cold, constipation, deeper voice, urinating more frequently than usual, nausea or vomiting, abdominal pain
Motor/sensory neuropathy; Encephalitis; Myasthenic syndrome/myasthenic gravis or Guillain-Barre syndrome	Numbness or tingling, weakness, confusion, headache, forgetfulness, changes in mood or behavior, fever, increased sensitivity to light, neck stiffness
Ocular Inflammation	Changes in vision (blurry vision; double vision; other vision changes), eye pain, eye redness, eyelid swelling
Pancreatitis	Nausea or vomiting, abdominal pain
Infection	Fever, other signs of infection
Musculoskeletal inflammation	New or worsening joint symptoms, muscle weakness or pain

irAE: immune-related adverse event

10.10 Appendix 10: Dose Modification and Toxicity Management for Immune-related Adverse Events

AEs associated with pembrolizumab exposure may represent an immune-related response. These irAEs may occur shortly after the first dose or several months after the last dose of pembrolizumab treatment and may affect more than one body system simultaneously. Therefore, early recognition and initiation of treatment is critical to reduce complications. Based on existing clinical study data, most irAEs were reversible and could be managed with interruptions of pembrolizumab, administration of corticosteroids and/or other supportive care. For suspected irAEs, ensure adequate evaluation to confirm etiology or exclude other causes. Additional procedures or tests such as bronchoscopy, endoscopy, skin biopsy may be included as part of the evaluation. Dose modification and toxicity management guidelines for irAEs associated with pembrolizumab are provided in [Table 16](#).

Based on the mechanism of action of ASP0739, immune-related adverse reactions (e.g., fever, headache, fatigue, hot flashes, diarrhea and muscular and joint pain) should be considered (see Section [2.3.1](#)) and managed as required per SOC. In case of such events, ensure adequate evaluation to confirm etiology or exclude other causes. In addition, the study medical monitor should be contacted to discuss event monitoring, follow up and study treatment management.

Table 16 Dose Modification and Toxicity Management Guidelines for Immune-related Adverse Events Associated with Pembrolizumab

General instructions:

1. Severe and life-threatening irAEs should be treated with intravenous corticosteroids followed by oral steroids. Other immunosuppressive treatment should begin if the irAEs are not controlled by corticosteroids.
2. Pembrolizumab must be permanently discontinued if the irAE does not resolve or the corticosteroid dose is not ≤ 10 mg/day within 12 weeks of the last pembrolizumab treatment.
3. The corticosteroid taper should begin when the irAE is \leq grade 1 and continue at least 4 weeks.
4. If pembrolizumab has been withheld, pembrolizumab may resume after the irAE decreased to \leq grade 1 after corticosteroid taper.

Table continued on next page

irAEs	Toxicity grade (CTCAE v5.0)	Action with pembrolizumab	Corticosteroid and/or other therapies	Monitoring and follow-up
Pneumonitis	Grade 2	Withhold	
 Administer corticosteroids (initial dose of 1 to 2 mg/kg prednisone or equivalent) followed by taper Add prophylactic antibiotics for opportunistic infections 	
 Monitor participants for signs and symptoms of pneumonitis Evaluate participants with suspected pneumonitis with radiographic imaging and initiate corticosteroid treatment
	Recurrent Grade 2, Grade 3 or 4	Permanently discontinue		
Diarrhea/Colitis	Grade 2 or 3	Withhold	
 Administer corticosteroids (initial dose of 1 to 2 mg/kg prednisone or equivalent) followed by taper 	
 Monitor participants for signs and symptoms of enterocolitis (i.e., diarrhea, abdominal pain, blood or mucus in stool with or without fever) and of bowel perforation (i.e., peritoneal signs and ileus) Participants with \geq grade 2 diarrhea suspecting colitis should consider GI consultation and performing endoscopy to rule out colitis Participants with diarrhea/colitis should be advised to drink liberal quantities of clear fluids. If sufficient oral fluid intake is not feasible, fluid and electrolytes should be substituted via IV infusion
	Recurrent Grade 3 or Grade 4	Permanently discontinue		
AST or ALT elevation or Increased Bilirubin	Grade 2 ^a	Withhold	
 Administer corticosteroids (initial dose of 0.5 to 1 mg/kg prednisone or equivalent) followed by taper 	
 Monitor with liver function tests (consider weekly or more frequently until liver enzyme value returned to baseline or is stable)
	Grade 3 ^b or 4 ^c	Permanently discontinue	
 Administer corticosteroids (initial dose of 1 to 2 mg/kg prednisone or equivalent) followed by taper 	

Table continued on next page

irAEs	Toxicity grade (CTCAE v5.0)	Action with pembrolizumab	Corticosteroid and/or other therapies	Monitoring and follow-up
Type 1 diabetes mellitus (T1DM) or Hyperglycemia	New onset T1DM or Grade 3 or 4 hyperglycemia associated with evidence of β -cell failure	Withhold ^d	
 Initiate insulin replacement therapy for participants with T1DM Administer anti-hyperglycemic in participants with hyperglycemia 	
 Monitor participants for hyperglycemia or other signs and symptoms of diabetes
Hypophysitis	Grade 2	Withhold	
 Administer corticosteroids and initiate hormonal replacements as clinically indicated 	
 Monitor for signs and symptoms of hypophysitis (including hypopituitarism and adrenal insufficiency)
	Grade 3 or 4	Withhold or permanently discontinue ^d		
Hyperthyroidism	Grade 2	Continue	
 Treat with non-selective beta-blockers (e.g., propranolol) or thionamides, as appropriate 	
 Monitor for signs and symptoms of thyroid disorders
	Grade 3 or 4	Withhold or permanently discontinue ^d		
Hypothyroidism	Grade 2, 3, 4	Continue	
 Initiate thyroid replacement hormones (e.g., levothyroxine or liothyronine) per standard of care 	
 Monitor for signs and symptoms of thyroid disorders
Nephritis: grading according to increased creatinine or acute kidney injury	Grade 2	Withhold	
 Administer corticosteroids (prednisone 1 to 2 mg/kg or equivalent) followed by taper 	
 Monitor changes of renal function
	Grade 3 or 4	Permanently discontinue		
Myocarditis	Grade 1 or 2	Withhold	
 Based on severity of AE administer corticosteroids 	
 Ensure adequate evaluation to confirm etiology and/or exclude other causes
	Grade 3 or 4	Permanently discontinue		
All Other immune-related AEs	Persistent Grade 2	Withhold	
 Based on severity of AE administer corticosteroids 	
 Ensure adequate evaluation to confirm etiology or exclude other causes
	Grade 3	Withhold or discontinue based on the event ^e		
	Recurrent Grade 3 or Grade 4	Permanently discontinue		

AE: adverse event; ALT: alanine aminotransferase; AST: aspartate aminotransferase; CTCAE: common terminology criteria for adverse events; GI: gastrointestinal; irAE: immune-related adverse event; IV: intravenous; T1DM: Type 1 diabetes mellitus; ULN: upper limit of normal

Footnotes continued on next page

^aAST/ALT: > 3.0 to 5.0 × ULN if baseline normal; > 3.0 to 5.0 × baseline, if baseline abnormal; bilirubin: > 1.5 to 3.0 × ULN if baseline normal; > 1.5 to 3.0 × baseline if baseline abnormal

^bAST/ALT: > 5.0 to 20.0 × ULN, if baseline normal; > 5.0 to 20.0 × baseline, if baseline abnormal; bilirubin: > 3.0 to 10.0 × ULN if baseline normal; > 3.0 to 10.0 × baseline if baseline abnormal

^cAST/ALT: > 20.0 × ULN, if baseline normal; > 20.0 × baseline, if baseline abnormal; bilirubin: > 10.0 × ULN if baseline normal; > 10.0 × baseline if baseline abnormal

^dThe decision to withhold or permanently discontinue pembrolizumab is at the discretion of the investigator or treating physician. If control achieved or ≤ grade 2, pembrolizumab may be resumed.

^eEvents that require discontinuation include but are not limited to: Guillain-Barre Syndrome, encephalitis, Stevens-Johnson Syndrome and toxic epidermal necrolysis.

10.11 Appendix 11: Dose Modification and Toxicity Management of Infusion Reactions Related to Pembrolizumab

Pembrolizumab may cause severe or life-threatening infusion-reactions including severe hypersensitivity or anaphylaxis. Signs and symptoms usually develop during or shortly after drug infusion and generally resolve completely within 24 hours of completion of infusion. Dose modification and toxicity management guidelines on pembrolizumab associated infusion reaction are provided in [Table 17](#).

Table 17 Pembrolizumab Infusion Reaction Dose Modification and Treatment Guidelines

NCI-CTCAE Grade	Treatment	Premedication at Subsequent Dosing
Grade 1 Mild reaction; infusion interruption not indicated; intervention not indicated	
Increase monitoring of vital signs as medically indicated until the participant is deemed medically stable in the opinion of the investigator.	None
Grade 2 Requires therapy or infusion interruption but responds promptly to symptomatic treatment (e.g., antihistamines, NSAIDs, narcotics, IV fluids); prophylactic medications indicated for \leq 24 hours.	
Stop Infusion.Additional appropriate medical therapy may include but is not limited to:
IV fluidsAntihistaminesNSAIDsAcetaminophenNarcoticsIncrease monitoring of vital signs as medically indicated until the participant is deemed medically stable in the opinion of the investigator.If symptoms resolve within 1 hr of stopping drug infusion, the infusion may be restarted at 50% of the original infusion rate (e.g., from 100 mL/hr. to 50 mL/hr.). Otherwise dosing will be held until symptoms resolve and the participant should be premedicated for the next scheduled dose. 
Participants who develop grade 2 toxicity despite adequate premedication should be permanently discontinued from further study drug treatment
	Participant may be premedicated 1.5 hours (\pm 30 min) prior to infusion of pembrolizumab with: Diphenhydramine 50 mg po (or equivalent dose of antihistamine). Acetaminophen 500 to 1000 mg po (or equivalent dose of analgesic).

Table continued on next page

NCI-CTCAE Grade	Treatment	Premedication at Subsequent Dosing
Grades 3 or 4 Grade 3: Prolonged (i.e., not rapidly responsive to symptomatic medication and/or brief interruption of infusion); recurrence of symptoms following initial improvement; hospitalization indicated for other clinical sequelae (e.g., renal impairment, pulmonary infiltrates) Grade 4: Life-threatening; pressor or ventilator support indicated	
• Stop Infusion.• Additional appropriate medical therapy may include but is not limited to:
• Epinephrine†• IV fluids• Antihistamines• NSAIDs• Acetaminophen• Narcotics• Oxygen• Pressors• Corticosteroids• Increase monitoring of vital signs as medically indicated until the participant is deemed medically stable in the opinion of the investigator.• Hospitalization may be indicated. 
†In cases of anaphylaxis, epinephrine should be used immediately. Participant is permanently discontinued from further study drug treatment.
	

Appropriate resuscitation equipment should be available at the bedside and a physician readily available during the period of drug administration. For further information, please refer to the Common Terminology Criteria for Adverse Events v5.0 (CTCAE) at <http://ctep.cancer.gov>

hr: hour; NCI: National Cancer Institute; NSAID: nonsteroidal anti-inflammatory drug

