- The safety in the expansion cohorts will be monitored using Bayesian logistic model based on all DLT data obtained up to that time from both escalation cohorts and expansion cohorts and drug-related TEAEs leading to death. Safety monitoring with these models will be started when an expansion cohort is opened. Enrollment in expansion cohorts may be held based on the criteria described in [Section 9 Statistical Considerations].

The potential risk of irAEs and IRRs may be mitigated by closely monitoring participants' symptoms, signs and clinical laboratory test results to facilitate early identification and management, as per the guidelines in [Section 10.8 Appendix 8: Infusion Reaction Dose Modification and Treatment (Guidelines for ASP0739 and Pembrolizumab); Section 10.9 Appendix 9: Monitoring of Pembrolizumab Potential Immune-related Adverse Events; Section 10.10 Appendix 10: Dose Modification and Toxicity Management for Immune-related AEs; and Section 10.11 Appendix 11: Dose Modification and Toxicity Management of Infusion Reactions Related to Pembrolizumab]. The management of such toxicities should be based on institutional SOC and published guidelines, as appropriate based on investigator judgment, and on the protocol instructions regarding interruption or discontinuation of treatment.

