6.8 Concomitant Therapy

The following treatments are prohibited during the study:

- The use of systemic steroids (> 30 mg per day of hydrocortisone or > 10 mg per day of prednisone or equivalent) is not allowed during study treatment unless needed to manage AEs related to study treatment. The use of topical, ocular, intra-articular, intranasal, and inhalational corticosteroids (with minimal systemic absorption) is allowed. Physiologic replacement doses of systemic corticosteroids (≤ 30 mg per day of hydrocortisone or ≤ 10 mg per day of prednisone or equivalent) are permitted. Corticosteroids for prophylaxis (e.g., contrast dye allergy) or for brief treatment of conditions not related to study treatment (e.g., delayed-type hypersensitivity reaction caused by a contact allergen) is also allowed. Corticosteroids to manage irAEs are permitted.
- Immunosuppressive agents including but not limited to, high dose steroids, mammalian target of rapamycin inhibitors (e.g., rapamycin) or mycophenolate mofetil.
- Investigational agents other than ASP0739 and pembrolizumab.
- Any other cancer directed therapies are prohibited during the study with ASP0739 and ASP0739 and pembrolizumab, including chemotherapy, biologic therapy, radiation therapy or surgery.
 - *Palliative (limited field) radiation therapy:* for bone metastases is allowed. Study treatment should be interrupted during radiation therapy. The use of bisphosphonates and receptor activator of nuclear factor kappa-B ligand inhibitors for bone metastases is allowed if initiated prior to screening.
- Vaccines: Live vaccines are prohibited while the participant is receiving study treatment and for 30 days after last dose of study treatment. Examples of live vaccines include, but are not limited to, the following: measles, mumps, rubella, chicken pox, yellow fever, seasonal flu, H1N1 flu, rabies, bacillus Calmette-Guérin and typhoid vaccine.
 - COVID-19 prevention is allowed if non-live vaccines are to be used. In cases where a live vaccine is needed for COVID-19 prevention, please contact the medical monitor for discussion.

Refer to [Section 10.5 Appendix 5: List of Excluded Concomitant Medications] for a detailed list of drug classes and/or specific medications that are prohibited during participation in the study.

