10.5 Appendix 5: List of Excluded Concomitant Medications

10.5.1 Concomitant Medications

The following list describes concomitant medications that are prohibited. This list should not be considered all inclusive. If there are concerns or questions about concomitant use of any drugs listed below, discussion with the medical monitor is strongly encouraged.

Drug Type	Generic Drug Name
Corticosteroids*	Dexamethasone Prednisone (Deltasone, Orasone, Predone, RAYOS, Sterapred, etc.)
Interferon/polyethylene-interferon	
Immunosuppressive Agents	Abatacept (Orencia, etc.) Adalimumab (Humira, etc.) Anajunra (Kineret, etc.) Azathioprine (Azasan, Imuran, etc.) Budesonide (Entocort EC, etc.) Certolizumab (Cimzia, etc.) Cyclosporine (Neoral, Sandimmune, SangCya, etc.) Etanercept (Enbrel, etc) Everolimus (Afinitor, Zortress, etc.) Golimumab (Simponi, etc.) Infliximab (Remicade, etc.) Ixekizumab (Taltz, etc.) Leflunomide (Arava, etc.) Mycophenolate (CellCept, Myfortic, etc.) Natalizumab (Tysabri, etc.) Prednisolone (Millipred, etc.) Rituximab (Rituxan, etc.) Secukinumab (Cosentyx, etc.) Sirolimus (Rapamune, etc.) Tocilizumab (Actemra, etc.) Tofacitinib (Xeljanz, etc.) Ustekinumab (Stelara, etc.) Vedolizumab (Entyvio, etc.)

*The use of high dose system corticosteroids are prohibited, with the exception of immune-related AEs.

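### Table 16 directs non-steroid immunosuppression for severe pembrolizumab irAEs not controlled by corticosteroids, but Section 6.8 and Appendix 5 prohibit those agents and exempt only corticosteroids

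*Protocol*

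**What the plan says.** **The direction.** Table 16 in Appendix 10 of the protocol (Section 10.10) covers irAEs associated with pembrolizumab. Its first general instruction has severe and life-threatening events treated with intravenous and then oral steroids, and continues: "Other immunosuppressive treatment should begin if the irAEs are not controlled by corticosteroids".

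**The prohibition.** Section 6.8 opens its list with "The following treatments are prohibited during the study". The second bullet of that list reads "Immunosuppressive agents including but not limited to, high dose steroids, mammalian target of rapamycin inhibitors (e.g., rapamycin) or mycophenolate mofetil". The section then refers to Appendix 5 (Section 10.5.1) for named drugs. The Immunosuppressive Agents row there includes infliximab, mycophenolate, tocilizumab and vedolizumab.

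**The exemptions.** The first bullet of Section 6.8 ends with "Corticosteroids to manage irAEs are permitted". The Appendix 5 footnote says "The use of high dose system corticosteroids are prohibited, with the exception of immune-related AEs", and its asterisk stands on the Corticosteroids row only.

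**The consequence for study treatment.** Section 8.1 lists the need for a prohibited concomitant treatment, in the investigator's opinion, among the reasons for which study treatment must be discontinued. Section 8.2 keeps participants who discontinue treatment in the study for follow-up.

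**The concern.** The protocol provides for irAE care in two steps, steroids first and another immunosuppressant if steroids fail. The concomitant-therapy rules make room only for the first step. An investigator with a participant in severe steroid-uncontrolled colitis finds one table saying that a second agent should be started, and another section and an appendix saying that the agent is prohibited.

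Two things are at stake. One is the clarity of a safety instruction at a point where Appendix 10 itself calls early treatment critical. The other is the deviation record. SAP Section 6.2.2 has a category, PD4, for excluded concomitant treatment, and rescue treatment that the protocol directs could be counted there as non-compliance.

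**Working it through.** The plan states no figure on this point, so the check is a comparison of texts with a few hand counts.

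**1. Does the ban cover what Table 16 directs?** Section 6.8 prohibits immunosuppressive agents as an open-ended class. The Immunosuppressive Agents row of Appendix 5 names 23 drugs. Two are corticosteroids (budesonide and prednisolone), so 23 − 2 = 21 are not. Once steroids have failed, any agent among these 21 that a site would choose is on the prohibited list.

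**2. Is any of the 21 exempted for irAEs?** Both exemptions, at the end of the first bullet of Section 6.8 and in the Appendix 5 footnote, name corticosteroids only. The count of exempted non-steroid agents is 0 of 21.

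**3. Does another section lift the ban?**

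- Section 2.3.2: "The management of such toxicities should be based on institutional SOC and published guidelines, as appropriate based on investigator judgment". It sets this beside the protocol's own rules on interrupting or stopping treatment and says nothing about prohibited medications.
- Appendix 5 encourages discussion with the medical monitor. It grants no exception, and Section 7 rules out prospective waivers.
- Section 10.3.9 lets an investigator take urgent safety measures without prior approval. It defines these as interventions outside the protocol, whereas the treatment here is one that Table 16 directs.
- Section 8.1 decides what happens to study treatment (it stops). It does not say that the drug may be given, and under Section 8.2 the participant remains in the study, which is the period the ban names.

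**4. How do Table 16 and Section 8.1 fit together?** In a first grade 3 colitis, Table 16 withholds pembrolizumab, and general instruction 4 allows it to resume once the event has settled. If a prohibited agent is needed, Section 8.1 requires a permanent stop. The mandatory rule overrides the permissive one, so a site can obey both, but neither place refers to the other.

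**5. What would an exemption alone do?** An exempted drug is no longer prohibited, so the Section 8.1 trigger no longer applies. Resumption under general instruction 4 would then govern first grade 3 colitis by default. An exemption added without a statement on stopping would remove a safeguard without saying so.

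**The case against.** The strongest reply is that the protocol already has a workable sequence: the need arises under Table 16, Section 8.1 stops study treatment, and the drug is then given. On this view the ban cannot sensibly bind after treatment ends, because the same list in Section 6.8 bans other cancer therapy while the follow-up schedule expects participants to start it. This is a sensible reading, and many sites would probably act on it. But the reader has to supply it. The text does not end the ban when treatment stops, and Table 16 does not say that second-line immunosuppression entails a permanent stop.

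A second reply is that a literal reading proves too much. Prednisolone and budesonide stand in the row without the asterisk, and the second bullet of Section 6.8 bans high-dose steroids with no exception of its own. This shows loose drafting. For corticosteroids, however, the first bullet of Section 6.8 supplies the answer, and there is no counterpart for the other 21 agents.

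A third reply concerns the deviation record, and here the objection stands in part. Section 7 defines a deviation as a departure from the design or procedures in the protocol, and Table 16 is itself such a procedure. A reader might infer that every use would be logged under PD4. The documents support only that it could be.

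Delay to care is likewise a possibility and not something the documents show. The instruction closest to the bedside decision is clear, and the medical monitor and urgent-measure provisions would help in practice.

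**Conclusion.** The point holds as an internal contradiction in the safety instructions: wrong as written, low severity. Table 16 directs treatment that Section 6.8 and Appendix 5 prohibit, and no text in either document exempts it.

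Its reach is limited to the planned combination therapy, because Table 16 concerns pembrolizumab. The SAP introduction says that the study ended early and that no combination treatment was given, so the realised effect is none. No endpoint or analysis changes.

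A reader might take the planned 158 combination participants (9 + 149, protocol Section 9.2), or the 7 of 10 event categories in Table 16 that list corticosteroids, as the size of the problem. Neither is. The first is planned enrolment, and the second shows only where the conflict could arise. The documents give no rate of steroid-uncontrolled irAEs, so no number of affected participants can be stated.

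The conclusion rests on reading the ban as worded, for the duration of the study. If it is read as ending with study treatment, what remains is a missing link between Table 16 and Section 8.1, which the same fix would close.

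**What to change.** Make three changes together in any amendment or reuse of this protocol:

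1. In the second bullet of Section 6.8, add: except when used to manage an irAE not controlled by corticosteroids (see Table 16).
2. Put the same exception as a footnote on the Immunosuppressive Agents row of Appendix 5.
3. State in Table 16 whether pembrolizumab and ASP0739 are permanently discontinued after such treatment. Keep the mandatory stop that Section 8.1 now imposes as the default unless the sponsor decides otherwise.

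The third part is not optional, because the first two switch off the Section 8.1 trigger. Stopping is a defensible default: Section 4.2 excludes participants with HIV on the ground that a compromised immune system may affect the response to ASP0739.

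The cost is wording in three places and one sponsor decision on stopping or resuming. No procedures, data or participants are added.
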